#### 6.2.2 Treatment period

Each subject will receive a single dose of BI 1467335 or placebo from Day 1 to Day 28.

Study participants will be admitted to the trial site in the evening of day -1 and kept under close medical surveillance for at least 24 h following the first /last drug administration. The

subjects will be kept hospitalized from the evening of Day -1 to the morning of Day 4, the evening of Day 13 to the morning Day 17 and from the evening of Day 27 to the morning of Day 29. On all other time periods the study will be performed in an ambulatory fashion provided there are no medical reasons preventing the discharge from the unit.

For details on time points and procedures for collection of plasma and urine samples for PK analysis, refer to [Flow Chart](#) and [Section 5.5.2](#).

The safety measurements performed during the treatment period are specified in [Section 5.2](#) of this protocol and in the [Flow Chart](#). For details on time points for all other trial procedures, refer to the [Flow Chart](#). AEs and concomitant therapy will be assessed continuously from screening until the end of trial examination.

### **6.2.3 End of trial and follow-up period**

For AE assessment, laboratory tests, recording of ECG and vital signs, and physical examination during the end of trial period, see [Sections 5.2.2](#) to [5.2.5](#).

Subjects who discontinue treatment before the end of the planned treatment period should undergo the end of trial visit.

All abnormal values (including laboratory parameters) that are judged clinically relevant by the investigator will be monitored using the appropriate tests until a return to a medically acceptable level is achieved. Adverse events persisting after trial completion must be monitored until they have normalised or have been sufficiently characterised.

The end of the trial as a whole is defined by the 'last regular visit completed by last subject' or 'end date of the last open AE' or 'date of the last follow-up test' or 'date of an AE has been decided as sufficiently followed-up', whichever is latest.

## 7. STATISTICAL METHODS AND DETERMINATION OF SAMPLE SIZE

### 7.1 STATISTICAL DESIGN – MODEL

#### 7.1.1 Objectives

The primary objective of this trial is to investigate the safety and tolerability of BI 1467335 by using descriptive statistics for all endpoints comparing active dose groups to placebo. The primary endpoint is defined in [Section 5.2.1](#). Inferential statistics is not planned (as explained in [Section 7.2](#)).

The secondary objective is the exploration of the pharmacokinetics (PK) ( ) of BI 1467335. Endpoints as specified in [5.5.1](#) and [5.7.1](#) will be analysed by descriptive statistics. Secondary endpoints as defined in [Section 5.5.1.1](#) will be subjected to analysis of dose proportionality by use of the power model.

### 7.2 NULL AND ALTERNATIVE HYPOTHESES

Safety and tolerability of 3 different dose groups of BI 1467335 are to be determined on the basis of the investigated parameters in comparison to placebo. It is not planned to test any statistical hypotheses with regard to these variables in a confirmatory sense. Instead, they will be described in their entirety and evaluated by descriptive statistical methods.

Confidence intervals will be computed and will have to be interpreted in the perspective of the exploratory character of the study, i.e. confidence intervals are considered as interval estimates for effects.

### 7.3 PLANNED ANALYSES

Adherence to the protocol (such as inclusion/exclusion criteria, times of measurement, compliance with intake of trial medication, treatment dispensing errors, prohibited concomitant medication, completeness and consistency of data) will be checked. Important protocol violations (IPVs) will be identified no later than in the Report Planning Meeting and provided in the TSAP.

#### 7.3.1 Primary analyses

All treated subjects (that is, all subjects who received at least one dose of study drug), will be included in the treated set.

The primary endpoint will be analysed only descriptively on the treated set. For more details see [Section 7.3.3](#).

The secondary endpoints (refer to [Section 5.5.1](#)) will be calculated according to the BI Standard Operating Procedure (SOP) ‘Standards and processes for analyses performed within Clinical Pharmacokinetics/Pharmacodynamics’ [[001-MCS-36-472](#)].

Plasma and urine concentration data and parameters of a subject will be included in the statistical pharmacokinetic (PK) analyses if they are not flagged for exclusion due to a protocol violation relevant to the evaluation of PK (to be decided no later than in the Report Planning Meeting) or due to PK non-evaluability (as revealed during data analysis, based on the criteria specified below). Exclusion of a subject’s data will be documented in the CTR. Relevant protocol violations may be

- Incorrect trial medication taken, i.e. the subject received at least one dose of trial medication the subject was not assigned to
- Incorrect dose of trial medication taken
- Use of restricted medications.

Plasma and urine concentrations and/or parameters of a subject will be considered as non-evaluable, if for example

- the subject experienced emesis that occurred at or before two times median  $t_{max}$  of the respective treatment (Median  $t_{max}$  is to be determined excluding the subjects experiencing emesis),
- missing samples/concentration data at important phases of PK disposition curve.

The PK parameter analysis set (PKS) includes all subjects in the Treated Set (TS) who provide at least one PK parameter that was not excluded according to the description above. All statistical evaluations of PK parameters will be based on the PKS.

Excluded subjects will be listed with their individual plasma concentrations and individual pharmacokinetic parameters, however, will not be included in descriptive statistics for plasma concentrations, pharmacokinetic parameters or other statistical assessment.

#### Assessment of dose proportionality

Dose proportionality will be assessed using the pharmacokinetic endpoints  $AUC_{0-24}$ ,  $C_{max}$ ,  $AUC_{0-24,28}$  and  $C_{max,28}$  as specified in [5.5.1.1](#).

The basic model for the investigation of dose proportionality will be a power model that describes the functional relationship between the dose and PK endpoints.

$$\exp(Y_{ij}) = \alpha' * \exp(X_i)^\beta * \epsilon'_{ij}$$

The model consists of a regression model applied to log-transformed data. The corresponding ANCOVA model includes the logarithm of the dose as a covariate.

Together with  $\alpha' = \exp(\alpha)$  and  $\varepsilon'_{ij} = \exp(\varepsilon_{ij})$ , taking natural logarithms converts this model to a linear form as follows:

$$Y_{ij} = \alpha + \beta * X_i + \varepsilon_{ij}$$

where

$Y_{ij}$	logarithm of the pharmacokinetic endpoint for subject j at dose level i; where $i = 1, 2, 3, j = 1, 2, \dots, N$ ;
$\alpha$	intercept parameter;
$\beta$	slope parameter;
$X_i$	logarithm of dose i;
$\varepsilon_{ij}$	random error associated with subject j at dose level i (assumed to be independent and identically normally distributed).

This equation can be fit as a linear regression model.

Based on the estimate for slope parameter ( $\beta$ ), a 2-sided 95% CI for the slope will be computed. Perfect dose proportionality would correspond to a slope of 1. The assumption of a linear relationship between the log-transformed pharmacokinetic endpoint and the log-transformed dose will be checked.

If dose proportionality over the entire dose range investigated cannot be shown, an attempt will be made to identify dose range(s), where dose proportionality can be assumed.

When steady state is already reached after 14 days of treatment, dose proportionality will be also investigated for  $AUC_{0-24,14}$  and  $AUC_{0-24,28}$  together ( $C_{max,14}$  and  $C_{max,28}$  respectively) using the following model accounting for the repeated measurement per subject:

$$Y_{ijk} = \alpha + \beta * X_i + \gamma T_k + \varepsilon_{ijk}$$

where

$Y_{ijk}$	logarithm of the pharmacokinetic endpoint for subject j at dose level I on day k; where $i = 1, 2, 3, j = 1, 2, \dots, N$ ;
$\alpha$	intercept parameter;
$\beta$	slope parameter;
$X_i$	logarithm of dose i;
$T_k$	Categorical day variable where $T_k = 0$ when PK parameter is from day 14 and $T_k = 1$ when PK parameter is from day 28
$\varepsilon_{ijk}$	random error associated with subject j at dose level i (assumed to be independent and identically normally distributed).

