### 3. DESCRIPTION OF DESIGN AND TRIAL POPULATION

#### 3.1 OVERALL TRIAL DESIGN AND PLAN

[figure not shown]

This multiple-rising dose trial is designed as double-blind, randomised, and placebo-controlled within parallel dose groups.

A total of 36 healthy male and female subjects is planned to participate in the trial, according to at least 3 sequential groups comprising 12 subjects per group. However, additional subjects may be entered to allow testing of intermediate doses within the approved dose range on the basis of experience gained during trial conduct (as described in [Section 2.3](#)), i.e. the actual number of subjects entered may exceed 36 but no more than 48. Such changes may be implemented via non-substantial CTP Amendments.

Within each dose group, 9 subjects will receive the active drug and 3 will receive placebo. Only one dose is tested within each dose group.

The dose groups to be evaluated are outlined in [Table 3.1: 1](#) below.

Table 3.1: 1 Dose groups

Dose Group	1	2	3
Daily dose (mg)	10	15	20
Number of subjects	12	12	12
Subjects receiving placebo	3	3	3
Subjects receiving active drug	9	9	9
Subject number			
Subject replacement number			

The dose groups will be investigated consecutively in ascending order of doses, maintaining a time interval of at least 14 days between last dosing of the previous dose group and the first drug administration of the subsequent dose group. The decision to proceed to the next cohort at the same dose level or the next higher dose group will be based upon the safety, tolerability and PK of the preceding cohort or dose groups as described in [Section 2.3](#), [Section 3.1](#) and in [Section 3.3.4.1](#). The inclusion of the second cohort of the 10 mg dose group will be based exclusively on safety and tolerability including checking for individual stopping rules (see [Section 3.3.4.1](#)), but not on PK data.

A documented Safety Review must take place prior to inclusion of any new cohort and between dose groups. Furthermore, an unscheduled safety review meeting can be requested anytime for any reasonable cause by the Principal Investigator (or an authorised deputy) or the sponsor of the study, e.g. because of any unforeseen adverse events, etc. Dose escalation will only be permitted if no safety concerns exist in the opinion of the Principal Investigator

(or an authorised deputy) and the trial clinical monitor (or an authorised deputy) as described in [Section 2.3](#).

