### Linearity index

Linearity will be explored if data allow using the linearity index (LI) that will be computed as follows:

$$LI = \frac{AUC_{\tau,ss}}{AUC_{0-\infty}}$$

The  $AUC_{\tau,ss}$  can be  $AUC_{0-24,14}$  and/or  $AUC_{0-24,28}$  depending on when the steady state is reached. If steady state is not reached within the 28 days, no linearity index will be evaluated.

In order to construct a confidence interval for LI, a statistical model using  $AUC_{\tau,ss}$  and  $AUC_{0-\infty}$  will be set up: A linear model on the logarithmic scale including effects for 'subject' and 'AUC type' can be applied, where 'subject' is a random and 'AUC type' a fixed effect.

$$[1] \quad Y_{ij} = \mu + \tau_i + s_j + e_{ij}, \text{ where}$$

$Y_{ij}$  logarithm of the response (AUC after first dose and at steady state) for subject  $j$  and AUC type  $i$ ; where  $i = 1$  (after first dose) or  $2$  (at steady state) and  $j=1, 2, \dots, n$

$\mu$  the overall mean

$\tau_i$  the AUC type  $i$

$s_j$  the effect associated with subject  $j$  (random effect)

[figure not shown]
$e_{ij}$  random error associated with subject  $j$  at AUC type  $i$  (assumed to be independent and identically normally distributed).

A pairwise comparison of both areas via the log transformed difference

$$\log\left(\frac{AUC_{\tau,ss}}{AUC_{0-\infty}}\right) = \log(AUC_{\tau,ss}) - \log(AUC_{0-\infty})$$

will then be performed including calculation of a 2-sided 95% CI. The back transformed point estimate then represents the estimate of LI. Perfect linearity holds true if this index equals unity.

Generally, this model will be applied to each dose level separately. If there is evidence that the areas are comparable across dose levels, they can be analysed simultaneously. The corresponding model will then include the log transformed dose as (additional) covariate

Graphical displays

To support the analyses of dose proportionality, linearity and [REDACTED] graphical representations of the data might be created. These might include (but are not limited to) individual time-courses of trough and 1 h post-dose plasma concentrations and the (geometric) mean plasma concentration time profiles.

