
Rationale for change
		
The 10 mg dose group in this ongoing study 1386.8 has recently completed the 4 week treatment period. The evaluation is ongoing, preliminary data have become available. Overall, BI 1467355 was well tolerated. There were in particular no AEs considered to be dose limiting and no SAEs, all subjects completed the treatment period per protocol. There were no clinically relevant abnormalities with respect to safety laboratory, vital signs, or ECG. In particular there were no ECG findings suggesting adverse effects on the QT interval. Preliminary PK data obtained for the 10 mg dose level shows in all subjects an AUC exposure below Cmax and 1/10th of the AUC at NOAEL in the 1 month rats study, the initially defined exposure threshold not to be exceeded by subjects. Extrapolations based on the clinical PK data derived from the completed 10 mg dose group and the data obtained with the completed 2 week Phase I study suggest that with the next planned dose of 15 mg QD over 4 weeks some subjects may exceed the 1/10th AUC margin at the end of the 4 week treatment period. The estimated mean and the 95% prediction interval of Cmax extrapolation to 15 mg are still well below the Cmax at NOAEL. As steady state was not reached after 4 weeks of treatment with 10 mg BI 1467355 it is considered to be more appropriate to use a nonlinear fit for determination of the attainment of steady state. Additional data obtained with the 15 mg dose group are considered crucial to provide a safety margin regarding the assumed maximum efficacious dose of 10 mg QD in NASH patients. Since in the completed 10 mg dose group there were no safety signals precluding the continuation with the next higher dose it is considered to be justified to increase the initial exposure threshold from 1/10th AUC to ½ AUC at NOAEL obtained in the 4 week toxicology study in rats. It should

Number of global amendment		3
		be highlighted that all remaining stopping rules (individual discontinuation criteria or stopping rules for the whole study) will remain unchanged. In addition the study is conducted under close clinical monitoring (including central ECG reading) to early identify adverse safety signals. In context with the changes required for Amendment 3 a few remaining inconsistencies were also corrected.

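### The pooled Day 14/Day 28 dose-proportionality model claims to handle repeated measurements, but as printed it has no subject term and independent errors, so its slope CI can be too narrow

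*Protocol*

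**What the plan says.** Protocol Section 7.3.1, *Assessment of dose proportionality*, first sets out a power model with one value per subject for AUC0-24, Cmax, AUC0-24,28 and Cmax,28. It then adds a second model, to be used "When steady state is already reached after 14 days of treatment", in which the Day 14 and Day 28 values are analysed together, for AUC and for Cmax, "using the following model accounting for the repeated measurement per subject".

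The printed model is Y_ijk = α + β·X_i + γ·T_k + ε_ijk, where X_i is log dose and T_k is a 0/1 indicator for Day 28. The error is defined as "random error associated with subject j at dose level i (assumed to be independent and identically normally distributed"). The definition list contains no subject effect and no covariance structure.

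The next part of the same section, *Linearity index*, also has two AUC values per subject. There the model does carry a subject term, "where 'subject' is a random and 'AUC type' a fixed effect".

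**The concern.** The sentence and the equation say different things. The day effect lets the mean differ between Day 14 and Day 28, but it does not tie together two values from the same person. With independent errors and no subject term, those values are treated as coming from two different people. The error definition also repeats the wording of the single-day model, naming subject and dose level but not day, which suggests that it was carried over without being adapted.

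Dose varies only between subjects, so a second measurement on the same subject adds little information on the slope when the two values are strongly correlated. An analyst who fits the printed form would report a slope CI that looks tighter than the single-day intervals, partly because each subject is counted twice. In a trial that reads its CIs as interval estimates, the width of the interval is itself the result.

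**Working it through.** The protocol gives no standard error, power or sample-size figure for this model (Section 7.6 says the sample size is not based on a power calculation), so there is no stated figure to reproduce. The check asks what the printed model does to the slope CI.

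**Inputs**
- Doses of 10, 15 and 20 mg (Section 2.2).
- Nine active subjects per dose: "Within each dose group, 9 subjects will receive the active drug and 3 will receive placebo" (Section 3.1). Complete data give 27 subjects and 54 values.
- Two-sided 95% CI for the slope. Section 7.3.1 states this for the basic model; I assume it carries over to the pooled one.
- Within-subject correlation ρ: not given, so a range is shown.

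**Spread of log dose.** The logs are 2.3026, 2.7081 and 2.9957, with mean 2.6688. Sxx = 9 × (0.3662² + 0.0393² + 0.3269²) = 2.183. For 15 and 20 mg only, Sxx = 18 × 0.1438² = 0.372.

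**Variance of the slope.** With balanced data and equal variance σ² on both days:
- true variance = σ²(1+ρ) / (2·Sxx);
- variance in the printed model ≈ σ² / (2·Sxx), with 54 − 3 = 51 degrees of freedom;
- valid analysis: regression of subject means on log dose, with 27 − 2 = 25 degrees of freedom. For the slope this is equivalent to a random-subject model when data are complete.

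The printed standard error is therefore too small by about √(1+ρ). Large-sample coverage is 2Φ(1.96/√(1+ρ)) − 1. At ρ = 0.5 this is 2Φ(1.600) − 1 = 0.890.

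**Simulation** (400,000 runs per ρ, normal log values). The SE factor is √(1+ρ). Width ratio means the mean width of the valid interval divided by that of the printed one.

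| ρ | SE factor | Coverage, printed, 3 doses | Width ratio, 3 doses | Coverage, printed, 15 and 20 mg | Width ratio, 15 and 20 mg |
|---|---|---|---|---|---|
| 0 | 1.00 | 95.0% | 1.02 | 95.0% | 1.03 |
| 0.3 | 1.14 | 91.5% | 1.17 | 91.5% | 1.18 |
| 0.5 | 1.22 | 89.0% | 1.26 | 88.9% | 1.28 |
| 0.7 | 1.30 | 86.4% | 1.34 | 86.2% | 1.37 |
| 0.8 | 1.34 | 85.1% | 1.38 | 85.2% | 1.41 |
| 0.9 | 1.38 | 84.0% | 1.43 | 83.8% | 1.45 |

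The two-dose columns use 18 subjects and 36 values, with 33 degrees of freedom for the printed model and 16 for the valid one. The subject-level analysis covers 94.9% to 95.1% in every row. A separate simulation of the three-dose case (40,000 runs per setting) gives the same coverage to within 0.003. It also shows that the direction depends on the sign of ρ: at ρ = −0.3 the printed interval is too wide (coverage 97.9%).

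**Apparent gain from pooling.** With three doses and ρ = 0.9, the mean half-width is 0.943σ as printed, 1.344σ when valid and 1.380σ for Day 28 alone. The valid gain from pooling is 0.036σ; the printed model shows 0.437σ.

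**Absolute scale.** Assume a geometric CV of 30%, so that σ = √ln(1 + 0.30²) = 0.294. With three doses the half-width is about 0.28 as printed, against 0.35 (ρ = 0.5) to 0.40 (ρ = 0.9) when valid. With two doses it is about 0.67 to 0.68 as printed, against 0.87 to 0.98.

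**The case against.** The strongest reply is that this model may never be run and that nothing depends on it. The rationale for Amendment 3 (Section 11) states "As steady state was not reached after 4 weeks of treatment with 10 mg", so the Day 14 condition is in serious doubt for the three-dose version, to which the headline figures belong. The 15 and 20 mg scenario is my own; the protocol does not plan it. There even the valid interval is so wide around a slope of 1 that its reading would hardly change. Section 7.2 says that CIs "will have to be interpreted in the perspective of the exploratory character of the study". Day 14 parameters are not secondary endpoints, and escalation rests on preliminary PK and safety data, not on this slope.

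It can also be said that the intent is clear and the omission probably editorial, so that an analyst who follows the sentence gets a valid interval. The statistical analysis plan and protocol Section 7.3.2 were not available to me, and either may specify how repeated values are handled. The 95% CI is not expressly stated for the pooled model.

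All of this limits the consequence and stands to that extent. It does not remove the contradiction. The protocol does not leave the covariance open for a later document: it asserts independence, in the model introduced as handling the repeated measurements, and no passage available to me corrects it.

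**Conclusion.** The point holds. The equation and error definition of the pooled model contradict its stated purpose and should be corrected. If the printed form is fitted and a subject's two values are positively correlated, the nominal 95% slope CI covers roughly 84% to 91.5% for ρ between 0.9 and 0.3.

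The mismatch itself is certain from the text. The size rests on assumptions: a ρ that the protocol does not give (positive correlation is plausible for two exposures in one person), equal variance on both days, complete data, and a 95% CI carried over from the basic model. The consequence is confined to one conditional, exploratory analysis. The single-day models for the four secondary PK endpoints use one value per subject and are unaffected.

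**What to change.** Make the equation do what its introduction says, for both AUC and Cmax:

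- Add a random subject effect, Y_ijk = α + β·X_i + γ·T_k + s_j(i) + ε_ijk, as the linearity-index model already does, or state a within-subject covariance for the two days.
- Define ε_ijk for subject j at dose level i on day k. With the random effect, state independence only conditional on subject.
- Base the slope CI on between-subject degrees of freedom: 25 with complete data at three doses, 16 at two. The exact degrees-of-freedom method and the covariance choice can be left to the statistical analysis plan.

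The cost is one term and one reworded definition, with no extra data or subjects. The pooled interval becomes wider whenever the within-subject correlation is positive.

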### Linearity index

Linearity will be explored if data allow using the linearity index (LI) that will be computed as follows:

$$LI = \frac{AUC_{\tau,ss}}{AUC_{0-\infty}}$$

The  $AUC_{\tau,ss}$  can be  $AUC_{0-24,14}$  and/or  $AUC_{0-24,28}$  depending on when the steady state is reached. If steady state is not reached within the 28 days, no linearity index will be evaluated.

In order to construct a confidence interval for LI, a statistical model using  $AUC_{\tau,ss}$  and  $AUC_{0-\infty}$  will be set up: A linear model on the logarithmic scale including effects for 'subject' and 'AUC type' can be applied, where 'subject' is a random and 'AUC type' a fixed effect.

$$[1] \quad Y_{ij} = \mu + \tau_i + s_j + e_{ij}, \text{ where}$$

$Y_{ij}$  logarithm of the response (AUC after first dose and at steady state) for subject  $j$  and AUC type  $i$ ; where  $i = 1$  (after first dose) or  $2$  (at steady state) and  $j=1, 2, \dots, n$

$\mu$  the overall mean

$\tau_i$  the AUC type  $i$

$s_j$  the effect associated with subject  $j$  (random effect)

[figure not shown]
$e_{ij}$  random error associated with subject  $j$  at AUC type  $i$  (assumed to be independent and identically normally distributed).

A pairwise comparison of both areas via the log transformed difference

$$\log\left(\frac{AUC_{\tau,ss}}{AUC_{0-\infty}}\right) = \log(AUC_{\tau,ss}) - \log(AUC_{0-\infty})$$

will then be performed including calculation of a 2-sided 95% CI. The back transformed point estimate then represents the estimate of LI. Perfect linearity holds true if this index equals unity.

Generally, this model will be applied to each dose level separately. If there is evidence that the areas are comparable across dose levels, they can be analysed simultaneously. The corresponding model will then include the log transformed dose as (additional) covariate

Graphical displays

To support the analyses of dose proportionality, linearity and [REDACTED] graphical representations of the data might be created. These might include (but are not limited to) individual time-courses of trough and 1 h post-dose plasma concentrations and the (geometric) mean plasma concentration time profiles.

